- The PD Analysis Set is the group of subjects who have sufficient PD data to derive at least 1 PD parameter.

Efficacy Analyses

The FAS will be used as the primary population for all efficacy analyses, while the PPS will be used as the supportive population.

Analyses for Primary Efficacy Endpoints

The primary analysis will be based on an intent to treat philosophy without regard to adherence to treatment. The primary analysis of the change from baseline in CDR-SB at 24 months will be performed to compare elenbecestat 50 mg per day versus placebo using a linear mixed effects model for repeated measures (MMRM) on the FAS. The MMRM model will include fixed effects of treatment group, visit, treatment group by visit interaction, baseline CDR-SB, baseline CDR-SB by visit interaction, and randomization stratification variables (ie, region [7 levels], clinical dementia [yes, no], and concurrent AD medication use at randomization (Visit 2) [yes, no]). *ApoE4* status may be included in the model if appropriate. (revised per Amendment 05) An unstructured covariance matrix will be employed to model the covariance of within subject effect; if MMRM fails to converge then a covariance structure with fewer parameters from the following list will be employed according to the prespecified order in the list until the MMRM converges. The list of covariance structure will include Heterogeneous Toeplitz, Toeplitz, Heterogeneous Compound Symmetry, and Compound Symmetry. This primary analysis will include all observed post baseline data of the change from

baseline in CDR-SB without imputation of missing values. The treatment effect for elenbecestat versus placebo will be compared at 24 months based on MMRM model. The LS means and difference in LS means between elenbecestat treatment group and placebo, and corresponding 95% confidence interval (CI) will be presented.

The null hypothesis is that there is no difference in the mean change from baseline in CDR-SB at 24 months between elenbecestat 50 mg per day and placebo. The corresponding alternative hypothesis is that there is a difference in the mean change from baseline in CDR-SB at 24 months between elenbecestat 50 mg per day and placebo.

The primary analysis will be repeated to minimize the impact of change in concomitant AD medications where efficacy data after initiation of new AD medications and increase of current AD medications will be censored.

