The following sensitivity analysis will be conducted to evaluate the impact of missing data: the primary endpoint will be analyzed using analysis of covariance model (ANCOVA) after multiple imputation. The ANCOVA model will include baseline CDR-SB as a covariate, with treatment group, and randomization stratification variables as factors. *ApoE4* status may be included in the model if appropriate. Additional sensitivity analyses will be performed to assess the robustness of the missing at randomization assumption in the primary MMRM model.

Subgroup analysis (eg, stratification factors and *ApoE4* status) and additional sensitivity analysis for the primary endpoint will be performed as appropriate. (revised per Amendment 05)

Analyses for Key Secondary Efficacy Endpoints (revised per Amendment 05)

The key secondary analyses will be performed only if the primary analysis is significant. The treatment effect for elenbecestat 50 mg/day versus placebo, for each key secondary efficacy endpoint, will be tested using a sequential testing procedure at a significance level of 2-sided alpha = 0.05, ie., any test will start only if the test with higher hierarchical order is significant.

The change from baseline in ADCOMS at 24 months will be analyzed using the same MMRM model as the primary efficacy analysis to compare elenbecestat 50 mg per day versus placebo on the FAS, using baseline ADCOMS in the model.

The change from baseline in amyloid PET SUVR at 24 months will be analyzed using the same MMRM model as the primary efficacy analysis to compare elenbecestat 50 mg per day versus placebo on the FAS, using baseline amyloid PET SUVR in the model. The same analysis will be performed within study as key secondary efficacy endpoint analyses.

Analyses for Other Secondary Endpoints (revised per Amendment 05)

The change from baseline in CDR-SB and ADCOMS at 24 months will be analyzed using the same MMRM model as the primary analysis for subjects enriched by baseline PET SUVR between eg, 1.2 and 1.6 on the FAS.

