The sample size for this study is estimated for comparison of elenbecestat versus placebo with respect to a pooled analysis of studies E2609-G000-301 and E2609-G000-302 for the change from baseline in CDR-SB at 24 months. Based on the available data from the placebo group in Study BAN2401-G000-201 (a recently completed study with a comparable subject population), the mean and the standard deviation of the change from baseline in CDR-SB at 24 months in the placebo group are assumed to be 1.46 and 2.05, respectively, instead of 1.75 and 2.05, which are originally assumed by the available data from ADNI (of amyloid positive, MMSE equal or greater than 24, late MCI [global CDR=0.5, CDR memory box \geq 0.5]) is selected to estimate the mean and standard deviation of the change from baseline in CDR-SB at 24 months in the placebo group, which are 1.5 and 2.05, respectively. Therefore, assuming a 25% reduction in the mean change from baseline CDR-SB at 24 months for elenbecestat compared to placebo with common standard deviation of 2.05 and 30% dropout rate, a total sample size of 1900 subjects, 950 subjects in each treatment group, will be required to detect the treatment difference between elenbecestat and placebo using a 2-sample t test with 90% power at a significance level of 2 sided alpha =0.05.

The pooled data from 2 studies (E2609-G000-301 and E2609-G000-302) will comprise the total sample size of approximately 1900 subjects. At least 850 subjects will be randomized in each study. (revised per Amendment 05)

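### The MMRM fallback list admits two homogeneous-variance covariance structures with no robust standard error; if one were ever reached, the month-24 test could be anti-conservative.

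*Protocol*

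**What the plan says.** The current synopsis (Analyses for Primary Efficacy Endpoints) compares the arms at month 24 from an MMRM on observed data with an unstructured within-subject covariance. On non-convergence, a structure with fewer parameters "will be employed according to the prespecified order in the list until the MMRM converges". The order is given: "The list of covariance structure will include Heterogeneous Toeplitz, Toeplitz, Heterogeneous Compound Symmetry, and Compound Symmetry". Nothing is said there about the standard error to be used with a fallback structure. Section 9.7.1.6.1 of the protocol text marked as revised per Amendment 01 carries the same list.

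The rule reaches beyond the primary endpoint. For the first key secondary, "The change from baseline in ADCOMS at 24 months will be analyzed using the same MMRM model as the primary efficacy analysis". The same model is applied to CDR-SB and ADCOMS in the subset enriched by baseline PET SUVR and to the other continuous secondary endpoints, and analyses are repeated within each study.

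On variability, the Sample Size Rationale gives one SD, for the 24-month change: "with common standard deviation of 2.05 and 30% dropout rate". No SD is given for any earlier visit.

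**The concern.** CDR-SB is scored every 3 months, so the model has eight post-baseline visits. A change from baseline is zero for everyone at the start and normally spreads as subjects progress at different rates. The protocol's own slope analysis of this change score uses a random coefficient model, which points the same way.

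Toeplitz and Compound Symmetry have a single variance parameter. When the true variance rises, that parameter settles near an average over visits, below the month-24 value, and the model-based standard error at month 24 is too small. Dropout adds to this, because the late, more variable visits contribute fewer observations to the average. The order of the list matters too: a homogeneous Toeplitz fit that converged would be accepted before Heterogeneous Compound Symmetry was tried.

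At stake is the type I error of the primary comparison in the one situation the fallback rule is written for. A correction made after unblinding would be a post hoc change to the primary analysis.

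**Working it through.** **Inputs from the protocol.** SD 2.05 at month 24, 30% dropout, 950 per arm, two-sided 0.05, eight visits (months 3 to 24). **Assumed:** the SD at earlier visits and the correlation pattern. These are varied below.

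**Step 1: the plan's sample size.** The synopsis has placebo mean and SD that "in the placebo group are assumed to be 1.46 and 2.05, respectively", "assuming a 25% reduction in the mean change from baseline CDR-SB at 24 months for elenbecestat compared to placebo", and tests "using a 2-sample t test with 90% power at a significance level of 2 sided alpha =0.05". The difference is 0.25 × 1.46 = 0.365. Then n = 2 × (1.960 + 1.282)² × 2.05² / 0.365² ≈ 663 per arm. Dividing by 0.70 gives 948 per arm, 1896 in total, which agrees with "a total sample size of 1900 subjects, 950 subjects in each treatment group". (The same paragraph also gives a placebo mean of 1.5, which would lead to 1798. That is a separate matter.) The SD of 2.05 is thus the plan's working value at month 24.

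**Step 2: closed form, complete data.** Let Var(t) = c + (4.2025 − c) × t/24 for t = 3, 6, …, 24, where 4.2025 = 2.05². The mean of t/24 over the eight visits is 0.5625. A homogeneous structure uses the visit-averaged variance V = c + (4.2025 − c) × 0.5625. The ratio of model SE to true SE is r = √V / 2.05, and type I error is 2 × [1 − Φ(1.96 r)].

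| c | Month-3 SD | √V | r | Type I error |
|---|---|---|---|---|
| 0 | 0.72 | 1.54 | 0.75 | 0.142 |
| 0.6 | 1.02 | 1.62 | 0.79 | 0.121 |
| 1.5 | 1.36 | 1.74 | 0.85 | 0.097 |

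**Step 3: a second method.** For each fallback structure, take the large-sample maximum-likelihood fit under a true eight-visit covariance with SD 2.05 at month 24, then compare its model-based SE for the month-24 difference with the true SE. Month-3 SD ran from 0.7 to 1.5, with autoregressive-type, random-slope and mixed correlations, and dropout of 0% or 30% completely at random.

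| Structure | Type I error, no dropout | Type I error, 30% dropout |
|---|---|---|
| Toeplitz | 0.086 to 0.159 | 0.091 to 0.178 |
| Compound Symmetry | 0.086 to 0.180 | 0.108 to 0.208 |

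The SE is understated by about 12% to 36%. As the early SD approaches 2.05 the problem fades. At a month-3 SD of 1.8, Toeplitz gives 0.065 to 0.067 and Compound Symmetry 0.065 to 0.082. With a flat 2.05 everything is at 0.050, except Compound Symmetry with dropout at 0.064.

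**Step 4: simulation.** With 950 per arm, month-3 SD 1.0, lag-1 correlation 0.9 and 30% dropout, Step 3 predicts 0.137 (Toeplitz) and 0.154 (Compound Symmetry). Simulated rejection rates were 0.134 (1800 runs, pooling batches at 0.100 and 0.151) and 0.147 (2000 runs).

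**Step 5: what a remedy achieves.** In the same simulations a sandwich SE gave 0.047 (Toeplitz) and 0.042 (Compound Symmetry). Keeping only heterogeneous structures with model-based SEs is not enough. By the Step 3 method, Heterogeneous Compound Symmetry gives 0.038 to 0.068. Heterogeneous Toeplitz gives 0.050 when the true correlation is Toeplitz, but 0.070 to 0.105 under random-slope or random-walk covariances.

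**The case against.** The strongest objection is that the rule will probably never fire for the primary test. Unstructured needs 8 × 9 / 2 = 36 covariance parameters for about 1900 pooled subjects, and Heterogeneous Toeplitz must fail as well before a homogeneous structure is reached. This stands, and it limits the practical weight. A reader might infer that the month-24 confidence interval is too narrow as planned. The protocol does not support that: the planned analysis is unstructured and estimates the month-24 variance directly.

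A reader might also infer that amyloid PET, an optional substudy with a smaller sample, is the exposed endpoint. The schedule does not support that either. PET has two scheduled post-baseline times, 12 and 24 months. With two visits, unstructured and Heterogeneous Toeplitz are the same three-parameter model, and failure to fit it is very unlikely. ADCOMS is weak support too: two of its three component scales are given every 6 months, so it has four treatment-period visits and 4 × 5 / 2 = 10 parameters. The more plausible cases are CDR-SB within one study (at least 850 subjects) and CDR-SB in the SUVR-enriched subset, which lies outside the sequential testing of key secondaries.

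The SE estimator is often left to the SAP, which is not shown and could specify a sandwich SE. That is fair, and silence on it is not the finding. The finding is the ordered list, which the protocol itself fixes. The planned ANCOVA after multiple imputation would not share the averaged variance and might expose a discrepancy, but it is a sensitivity analysis and does not correct the primary p-value.

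**Conclusion.** The point holds as a conditional one. The list contains two homogeneous-variance structures, one of them ranked ahead of a heterogeneous alternative. If either were used with model-based standard errors while variance grew with time, two-sided type I error at month 24 would be about 0.09 to 0.21, or 1.7 to 4.2 times nominal. That range rests on assumed month-3 SDs of 0.7 to 1.5 rising to the stated 2.05 and on dropout completely at random; it is not a figure from the protocol. With flat variance the inflation is nil or small. The likelihood of reaching these structures is low for pooled CDR-SB and somewhat higher in the smaller CDR-SB analyses. It is a cheap correction worth making before unblinding, not a flaw in the planned primary analysis.

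**What to change.** Add one sentence to the protocol or SAP, covering every endpoint that uses the primary MMRM: any covariance structure other than unstructured is fitted with the empirical (sandwich) variance estimator. This is the essential part. In the same edit, remove Toeplitz and Compound Symmetry, or at least place them after both heterogeneous structures. Reordering or deletion alone is not sufficient, because Heterogeneous Toeplitz with model-based SEs can still reach about 0.07 to 0.105. Deletion remains worthwhile beside the sandwich SE, since that estimator repairs the standard error but not any bias from a misspecified covariance when dropout depends on earlier scores. There is no cost in data, visits or sample size.

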 - b. CDR global score of 0.5
 - c. CDR Memory Box score of 0.5 or greater
2. A history of subjective memory decline with gradual onset and slow progression over the last 1 year before Screening; this MUST be corroborated by a study partner
3. Cognitive impairment of at least 1 SD from age-adjusted norms in total recall or delayed recall on the ISLT.
4. Positive biomarker for brain amyloid pathology as indicated by at least 1 of the following:
 - a. PET assessment of amyloid imaging agent uptake into brain. Note: amyloid PET screens will be performed according to local regulatory guidelines and thus may be restricted for those subjects who are not suitable for lumbar puncture (LP) to obtain CSF for testing of eligibility.
 - b. CSF AD assessment(eg, tau:Aβ(1-42) ratio) (revised per Amendment 03)

NOTE: Subjects may undergo both the amyloid PET and CSF assessments, but need a positive amyloid result in only 1 of the 2 procedures to confirm eligibility. Subjects who consent to amyloid PET or CSF for eligibility purposes are not required to participate in the amyloid PET or CSF longitudinal substudies. Use of a historical amyloid positive PET (conducted within 12 months before the planned date of randomization) is acceptable for determination of eligibility but will not suffice for the baseline assessment if the subject wishes to consent to the amyloid PET longitudinal substudy. The historical imaging data must be made available to the sponsor. Historical CSF samples, if collected, processed, and stored under appropriate conditions and approved by the sponsor, may be analyzed to determine CSF amyloid positivity. (revised per Amendments 03 and 05).
5. Male or female subjects between 50 and 85 years of age, inclusive at the time of consent
6. If receiving an acetylcholinesterase inhibitor (AChEI) or memantine or both for AD, must be on a

stable dose for at least 12 weeks before Randomization. Treatment-naïve subjects with AD can be entered into the study.

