The rate of change over time (mean slope) based on change from baseline in the CDR-SB will be analyzed using linear mixed effects (LME) models for multivariate normal data derived from a random coefficient model (slope analysis), where the mean slope in each group depends on a continuous assessment time. The LME model will include treatment group, baseline CDR-SB, randomization stratification variables, assessment time, baseline CDR-SB-by-assessment time, and treatment group-by-assessment time. *ApoE4* status may be included in the model if appropriate.

Time to worsening of CDR scores by 24 months will be analyzed on the FAS using Cox regression model for treatment effect adjusting for randomization stratification factors. *ApoE4* status may be included in the model if appropriate. (revised per Amendment 05) Time to worsening of a CDR score

is defined as time from randomization to worsening of the CDR score (ie, the first worsening in 2 consecutive scheduled visits). For subjects whose CDR scores have not worsened by the end of the Treatment Period of the Core Study, the time to worsening of the CDR score will be censored at the date of last CDR assessment for these subjects.

Time to conversion to dementia for subjects who were not clinically staged as dementia at Baseline based on clinical diagnosis will be analyzed on the FAS using Cox regression model for treatment effect adjusting for randomization stratification factors. *ApoE4* status may be included in the model if appropriate. (revised per Amendment 05) Proportion of subjects with dementia diagnosis at 24 months will be estimated using Kaplan–Meier method based on time to conversion to dementia based on clinical diagnosis. Time to conversion to dementia for subjects who were not clinically staged as having dementia at Baseline based on clinical diagnosis is defined as time from randomization to conversion to dementia based on clinical diagnosis. For subjects without clinical dementia by the end of study, the time to conversion to dementia based on clinical diagnosis will be censored at the date of last dementia diagnosis.

The other continuous secondary efficacy endpoints as defined above will be analyzed using the same MMRM model as the primary efficacy analysis to compare elenbecestat 50 mg per day versus placebo on the FAS, using baseline value corresponding to the response variable in the model.

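### The Cox models for time to CDR worsening and time to dementia leave out baseline CDR-SB, which may cost some power on two non-key secondary endpoints

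*Protocol*

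**What the plan says.** In the Version 7.0 synopsis, under the analyses for other secondary endpoints, both time-to-event endpoints are analysed on the Full Analysis Set "using Cox regression model for treatment effect adjusting for randomization stratification factors". ApoE4 status may be added if appropriate. The stratification factors are region (7 levels), clinical dementia (yes/no) and concurrent AD medication (yes/no).

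Baseline CDR-SB appears in three other analyses of the same synopsis:

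- The primary MMRM lists "baseline CDR-SB, baseline CDR-SB by visit interaction, and randomization stratification variables".
- For the sensitivity analysis after multiple imputation, "The ANCOVA model will include baseline CDR-SB as a covariate".
- The slope model contains baseline CDR-SB and its interaction with assessment time.

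The CDR is administered at Visit 2 before the first dose, and membership of the Full Analysis Set requires a baseline primary efficacy measurement. Core Study entry requires, at Screening, a "CDR global score of 0.5". The conversion analysis is limited to subjects not staged as having dementia at Baseline.

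**The concern.** The protocol names the covariates of both Cox models, so this is a stated choice and not a detail left open. It passes over a severity measure that is already available in every analysed subject.

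Because entry requires a single global CDR value at Screening, the baseline global score carries little severity information. CDR-SB sums the six box scores from the same interview, and a subject with higher boxes is plausibly closer to the next global stage or to a dementia diagnosis. In the worsening model the dementia stratum may carry part of that information. In the conversion model it cannot, because nearly everyone has the same value. What remains is region and AD medication.

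In a Cox model, leaving out a prognostic covariate moves the estimated treatment hazard ratio toward 1 and lowers power, even under randomisation. At stake is the sensitivity of two secondary endpoints.

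**Working it through.** **The plan's own figure.** The protocol gives no event rate, hazard ratio or power for either Cox endpoint. Its only sample-size figure is 1900 for the pooled CDR-SB comparison, at "90% power at a significance level of 2 sided alpha =0.05" and "assuming a 25% reduction in the mean change from baseline CDR-SB at 24 months for elenbecestat compared to placebo". With placebo mean 1.46, SD 2.05 and 30% dropout:

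- Difference = 0.25 × 1.46 = 0.365
- n per arm = 2 × (1.960 + 1.2816)² × 2.05² / 0.365² = 663
- 663 / 0.70 = 948 per arm, total 1896, which matches 1900

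(The same paragraph also gives a placebo mean of 1.5. That yields 629 per arm, 899 after dropout and 1798 in total. This is a separate matter.)

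**Inputs for the Cox check.** From the protocol: N = 1900, 1:1 allocation, 30% dropout, 24 months, two-sided 5%. From the cap of about 25% with dementia: 0.75 × 1900 = 1425 for the conversion analysis. Assumed, because the documents give nothing: placebo 24-month event probability 0.30 or 0.45, conditional treatment hazard ratio (HR) 0.75 or 0.80, and HR per SD of baseline CDR-SB (θ) of 1.0, 1.3, 1.6 or 2.0.

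**Method.** The hazard is λ × θ^x × HR^treat, with x standard normal and time in units of 24 months. λ is set so that the average of 1 − exp(−λθ^x) equals the placebo event probability. Dropout is exponential at rate −ln 0.70, with censoring at 24 months. Each of 800 simulated trials per scenario was analysed by Cox regression with treatment alone and with treatment plus x.

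**Power (%) without → with the covariate:**

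| N | Placebo events | HR | θ = 1.0 | θ = 1.3 | θ = 1.6 | θ = 2.0 |
|---|---|---|---|---|---|---|
| 1900 | 0.30 | 0.75 | 83.0→83.4 | 81.2→81.2 | 82.0→84.0 | 79.1→84.4 |
| 1900 | 0.30 | 0.80 | 66.2→66.5 | 65.0→65.5 | 62.7→65.6 | 58.1→64.7 |
| 1900 | 0.45 | 0.75 | 95.8→95.9 | 96.1→96.0 | 94.1→96.1 | 92.4→95.8 |
| 1900 | 0.45 | 0.80 | 83.9→83.9 | 83.3→84.8 | 78.0→81.9 | 72.9→81.0 |
| 1425 | 0.30 | 0.75 | 75.5→75.6 | 72.9→73.9 | 69.4→71.9 | 66.2→73.3 |
| 1425 | 0.30 | 0.80 | 52.5→52.4 | 53.4→55.0 | 48.6→51.2 | 44.6→53.4 |
| 1425 | 0.45 | 0.75 | 89.4→89.2 | 86.3→87.1 | 89.2→91.6 | 81.8→88.9 |
| 1425 | 0.45 | 0.80 | 70.8→70.9 | 72.5→73.9 | 68.0→73.1 | 62.9→71.4 |
| Gain, points | | | −0.2 to 0.4 | −0.1 to 1.6 | 2.0 to 5.1 | 3.4 to 8.8 |

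At θ = 2.0 a conditional hazard ratio of 0.75 is estimated as 0.763 to 0.770 without the covariate, and 0.80 as 0.813 to 0.820.

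Cross-check by Schoenfeld's formula: 442 events at HR 0.80 give Φ(√(442/4) × 0.2231 − 1.96) = 0.650, against a simulated 0.662 at θ = 1.0.

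**With a dementia stratum in both models.** A second simulation (N = 1900, HR 0.80, 2,000 trials per cell) kept a 25% dementia stratum whose latent correlation with x was 0.5. Prognostic strength is expressed as the correlation with log event time, s/√(s² + π²/6) with s = ln θ:

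| Correlation | θ | 30% placebo events | 40% placebo events |
|---|---|---|---|
| 0.30 | 1.49 | 62.1→63.8 | 73.8→76.2 |
| 0.36 | 1.65 | 61.0→64.5 | 74.7→78.4 |
| 0.50 | 2.10 | 56.9→63.0 | 70.2→78.6 |

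The gains are 1.7 to 2.4, 3.5 to 3.7 and 6.1 to 8.4 points. Even with the stratum present they are of the same order as in the first table.

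**The case against.** The planned analysis is standard and valid. The protocol's habit is to adjust a continuous outcome for its own baseline, and CDR-SB is not the outcome of either Cox model: one uses the global CDR, the other a centrally reviewed clinical diagnosis. The omission therefore contradicts nothing in the plan. That stands, and the point is one of efficiency, not error.

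The size of the gain also rests on an input that the documents do not supply. Entry at global CDR 0.5 and MMSE of at least 24 narrows the range of CDR-SB, which could make it a weak predictor. The simulations use continuous event times, whereas the CDR is assessed every three months and worsening must be seen at two consecutive visits. They also leave out region, AD medication and ApoE4. These points limit the precision of the figures but do not reverse their direction.

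Several stronger readings go beyond the documents:

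- A reader might infer that the imputation model contains baseline CDR-SB. The protocol places it in the ANCOVA run after imputation and does not describe the imputation model.
- A reader might infer that baseline global CDR is the same for everyone. The requirement applies at Screening. The CDR is repeated at Visit 2, after a prerandomization phase of up to 50 days plus a 30-day window.
- A reader might take the shift of the hazard ratio toward 1 for bias. It is non-collapsibility: the two models estimate slightly different quantities, each valid.

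**Conclusion.** Both Cox models omit a baseline severity measure that is available in every analysed subject and used elsewhere in the plan. The case is strongest for time to conversion, where no stratification factor carries severity.

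The expected gain is about 0 to 2 points if baseline CDR-SB is weakly prognostic (HR per SD 1.3), 2 to 5 if moderately (1.6) and 3 to 9 if strongly (2.0). It is about zero if not prognostic at all. These ranges rest on the assumed event rates, treatment effects and prognostic strengths listed in the working. A gain of 6 to 8 points is tempting as a headline, but it needs a correlation of 0.5 with log event time, about HR 2.1 per SD, for which the documents give no support.

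Both endpoints are classed as other secondary, outside the sequential test of the key secondaries, and neither has a power target. Type I error and the primary and key secondary conclusions do not change. This is a small improvement worth making.

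**What to change.** Before unblinding, state that both Cox models adjust for baseline CDR-SB together with the stratification factors, and omit the dementia-staging term from the conversion model, where it does no work. Time to change of concomitant AD treatment is to be analysed like time to conversion, so say whether the change applies there as well.

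The cost is one phrase in the protocol or SAP and one term in the programs, with no new data. The small downside is interpretive: the reported hazard ratio becomes conditional on baseline CDR-SB as well as on the strata, so it is a slightly different quantity from the stratum-adjusted one. The report should say so.
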